Aim 2. Determine mediating effects of self-efficacy and outcomes expectation on PA and sedentary behavior outcomes of Active-Life. We hypothesize that positive changes in self-efficacy for overcoming barriers to LPA and outcomes expectations for exercise will mediate changes in the time spent in PA and sedentary behavior.

Secondary Aim. Determine short term and sustained effects of Active-Life vs active control on frailty indicators: strength, endurance, balance, walking speed and physical function. The working hypothesis is that the Active-Life group will have significantly higher scores (less frailty) on all frailty indicators after completion of Active-Life compared to the active control group and effects will be sustained at 3, 6 and 12 months.

This research addresses a key issue identified by the 2012 Institute of Medicine report: Living Well With Chronic Disease.³⁹ We will test an intervention to reduce the burden of chronic illness, targeting people with COPD, most of whom have multiple chronic conditions.⁴⁰ The intervention is aimed at physical inactivity, a risk factor for chronic disease. If this intervention is successful in reducing/delaying frailty it could have long reaching economic effects by decreasing health care utilization and the cost of care for people with COPD.

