- Subjects must have moderate to very severe airflow limitation. The forced expiratory volume in 1 second (FEV1) compared to predicted (% predicted) must be FEV1 < 80% predicted according to GOLD standards (moderate, 50%, \leq FEV1 < 80% predicted; Severe 30% \leq FEV1 < 50%; very severe, FEV1 < 30% predicted).¹⁶⁰
- Subjects must be \geq 50 years of age,
- COPD must be their major pulmonary problem,
- can have no other major health problems that limit PA and/or walking,
- must be clinically stable at the time of enrollment,
- must be sedentary with less than 30 minutes of moderate PA 5 days a week,
- must provide written medical clearance with permission to participate in the research.

Exclusion criteria.

- People will be excluded if they have participated in a structured exercise program or pulmonary rehabilitation within the last year.
- Major health problem that limits PA
- Will be excluded if unable to meet all the above inclusion criteria.

To insure a similar severity of disease and gender mix in each group, subjects will be randomly assigned to groups that are stratified according to gender and severity of airflow obstruction (i.e., stratified randomization). Screening will include pulmonary function tests, brief history and physical exam, 6-minute walk test and permission of their physician.

Subject recruitment is one of the most challenging components of this research. We have been successful in the past and we build on this experience by establishing a multifaceted and robust plan for recruitment. Subjects will be recruited from the following sources, see letters of support.

Table 6. Recruitment location and plan pool **Size of potential subject pool**

UM Health System. We will screen medical records and mail recruitment letters to potentially qualified people. For those who respond we will conduct an initial phone screening to determine preliminary eligibility, followed by in-person screening to determine final eligibility.	1800 patients with COPD documented by pulmonary function tests

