standard deviation of the mediator, and ρ was the correlation between the intervention and the mediator. We set type I error rate α at 0.05, type II error rate β at 0.2 (power = 0.8), the residual variance at 1, mediator variance at 1, and correlations between intervention and mediator range from 0.1 to 0.5. The effect size γ was determined using Cohen's definition of effect size from small (0.14) to medium (0.39)¹⁶². Evaluating our previous study, we expected to detect small to medium effect size ($\gamma = 0.26$). Therefore, when the correlation between the intervention variable and mediator was 0.3, we required 128 patients to reach 80% power. Because our past experience indicated 30% attrition, we proposed to enroll 183 patients at baseline to provide enough power to infer intermediate variables.

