Secondary Aim. To evaluate the short term and sustained effects of the Active-Life intervention, the linear mixed model (LMM) with a random intercept will be used to model the effect of the intervention. The random intercept in the LMM takes into account that the frailty indicators measured at baseline, 10 weeks; and 3, 6, and 12 months are correlated within the same individual. A number of response variables characterizing the effects of the intervention are considered, based on strength, endurance, physical function, balance, and walking speed. In addition to the binary indicator variable representing intervention or control, the demographic variables such as age, gender, and race will be added as covariates in the LMM to improve the precision of estimation. The intervention is claimed to be statistically significant if the p -value of the intervention variable is < 0.05 .

Strategies to address potential limitations.

Recruitment. We have used our state wide connections to establish a robust plan for subject recruitment. Travel distance is an important predictor of program completion,⁶³ so we will establish regional data collection sites in Grand Blanc, and Flint in addition to Ann Arbor. We require only a small space for training and all equipment is portable so all interventions and data collection can be performed on site. This will reduce the need for subjects to travel long distances for testing.

Retention activities. (a) At enrollment all subjects will be told that if they wish, they can participate in the alternative intervention after completing their assigned intervention and follow-up. This is to minimize subjects' disenchantment based on group assignment and to minimize attrition. We have taken this approach with two previous intervention studies and it dispels subjects' concerns about random assignment to groups. We will not conduct any data collection during the alternative intervention. In our experience a few people will take us up on this offer. (b) We will provide financial incentives for each data collection visit (\$25) and for each 7-days of PA data (\$50), but not for intervention visits because a financial incentive for training would limit generalizability of results. (c) To minimize the loss at follow-up, we will tell subjects that it is just as important that we study those who stop being active as those who continue with their PA.

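### The secondary-aim mixed model, as written, averages a null baseline difference into one arm term and cannot test short-term or sustained effects

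*Combined protocol and SAP*

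**What the plan says.** Under Specific Aims, the secondary hypothesis is tied to visits: better frailty scores than control once the program ends, and "effects will be sustained at 3, 6 and 12 months".

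The Secondary Aim paragraph of the Data Analysis Plan gives the model meant to answer this, a linear mixed model with a random intercept.

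- **Responses.** The random intercept "takes into account that the frailty indicators measured at baseline, 10 weeks; and 3, 6, and 12 months are correlated within the same individual". Five visits are listed, and baseline is one of them.
- **Fixed effects.** "In addition to the binary indicator variable representing intervention or control, the demographic variables such as age, gender, and race will be added as covariates". No others are named.
- **Decision rule.** "The intervention is claimed to be statistically significant if the" p-value of the arm variable falls below 0.05.

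The section on inclusion and exclusion criteria says that randomisation is "stratified according to gender and severity of airflow obstruction". Gender is in the model's covariate list; airflow severity is not.

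Aim 1, in the same Data Analysis Plan, is handled differently: a separate ANCOVA at each follow-up time, adjusted for baseline activity and for COPD severity among other covariates.

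**The concern.** With baseline among the responses and a single arm indicator, the arm coefficient is the difference between arms averaged over every visit, including one made before treatment starts. That is not the treatment effect at any visit, and it is pulled toward zero.

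Three consequences follow.

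1. Every frailty indicator gets a diluted estimate.
2. The baseline measurement is used as an outcome, not to remove between-person variance. The arm term carries the full between-person variance, which is costly when repeated measures are highly correlated.
3. An effect that fades after week 10 and one that appears only at month 12 give the same coefficient, so the sustained-effect hypothesis has no test.

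The third point matters for this program. The Preliminary Studies section reports that light-activity gains in the team's earlier trial had gone by 12 months. It also reports that the pilot six-minute walk gain fell from 116 to 63 feet within two months of the program's end.

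**Working it through.** **The plan's own sample size.** The only sizing is for the mediator test: (1.96 + 0.842)² × 1 / [0.26² × (1 − 0.3²)] = 127.6, so 128 subjects, and 128/0.70 = 183 enrolled. Both figures reproduce with a two-sided 0.05 level. Neither concerns the secondary aim, for which no power is given.

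**Inputs.** From the plan: 64 per arm, five visits, 70% retention at the end of the intervention. Assumed: effect d in SD units, equal variance at each visit, and a common correlation r between visits. The plan gives neither d nor r for the frailty indicators as an arm comparison.

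**What the arm term estimates (complete data).** For a balanced random-intercept model with an arm term only:

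- Coefficient = (0 + d at week 10 + d at month 3 + d at month 6 + d at month 12)/5
- Constant effect: 4d/5 = 0.80d, whatever r is
- Week 10 only, or month 12 only: d/5 = 0.20d

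**Standard errors (n per arm, SD units).**

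- As written: √[(2/n)(1 + 4r)/5]
- Baseline-adjusted mean of four follow-ups: √[(2/n)((1 + 3r)/4 − r²)]
- Baseline-adjusted contrast at one visit: √[(2/n)(1 − r²)]

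At d = 0.3, r = 0.7, n = 64:

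- As written: estimate 0.24, SE 0.154, power 0.34
- Mean of four follow-ups: estimate 0.30, SE 0.094, power 0.89
- Single visit: estimate 0.30, SE 0.126, power 0.66
- Effect at week 10 only: the arm term estimates 0.06, power 0.07, against 0.66 for the week-10 contrast

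Power over a range, for a constant effect with 64 per arm:

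| d | r | As written | Single visit, adjusted | Mean of four, adjusted |
|---|---|---|---|---|
| 0.3 | 0.5 | 0.42 | 0.50 | 0.79 |
| 0.3 | 0.7 | 0.34 | 0.66 | 0.89 |
| 0.3 | 0.8 | 0.32 | 0.81 | 0.96 |
| 0.5 | 0.3 | 0.93 | 0.84 | >0.99 |
| 0.5 | 0.5 | 0.83 | 0.90 | >0.99 |
| 0.5 | 0.7 | 0.74 | 0.98 | >0.99 |

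**With dropout.** Suppose 30% of 183 leave before week 10 and contribute baseline only. A completer's five-visit mean has weight w = 1/(r + (1 − r)/5); a baseline-only subject has weight 1. The coefficient is 0.7w × 0.8d/(0.7w + 0.3). At r = 0.7, w = 1.316, giving 0.737d/1.221 = 0.603d. For r = 0.5, 0.6 and 0.8 it is 0.636d, 0.619d and 0.588d. A simulation with 182 subjects (1,500 runs, r = 0.7, d = 0.3) gave a ratio of 0.60 and power 0.27, against 0.88 for the baseline-adjusted mean of the follow-ups.

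**Illustration from the pilot walk test.** The SDs at baseline and end of intervention (352 and 285 ft) with a change SD of 128 ft imply r = (352² + 285² − 128²)/(2 × 352 × 285) = 0.94. The two-month figures (342 and 129 ft) imply 0.93. Take SD 350 ft, r = 0.93 and 64 per arm, and treat the one-group pilot changes as arm differences: 116 ft at week 10 and 63 ft at each later visit.

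- As written: (0 + 116 + 63 + 63 + 63)/5 = 61 ft, SE 60 ft, power 0.17
- Baseline-adjusted contrasts: SE 23 ft, power above 0.99 at week 10 and 0.79 at month 12
- 116 ft at week 10 only, or at month 12 only: 23 ft either way, power 0.07

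**The case against.** The paragraph is short and is not a full model equation. Its stated purpose is to evaluate short-term and sustained effects, and its covariate sentence concerns precision, so visit terms may have been intended. But no section supplies them, and the rule reads one p-value on the arm variable. If arm-by-visit terms were added with baseline as the reference visit, that arm main effect would estimate the baseline difference. In simulation at r = 0.7 with a constant 0.5 SD effect, it averaged about zero. The text has to change on either reading.

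Four qualifications stand.

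- The 0.89 comparator is the mean of four follow-ups, which does not separate short-term from sustained effects either. The like-for-like figure for a visit contrast is 0.66. At r = 0.3 a single-visit contrast has less power than the diluted term (0.84 against 0.93 at d = 0.5), although it answers the right question.
- The dropout figures assume that all 30% leave before week 10. The Attrition paragraph's 70% retention at the end of the intervention supports this, but the same paragraph links attrition to the 12 months of follow-up. Later losses dilute less.
- This is a secondary aim. With no effect at any visit and complete data, the fault does not inflate type I error.
- Omitting COPD severity costs precision and is a lesser point.

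**Conclusion.** The concern holds and must be fixed. Followed as written, the model returns 80% of a constant effect with complete data. That figure rests only on five balanced visits, no true difference at baseline and no baseline adjustment. It returns about 59% to 64% if 30% of subjects contribute baseline only and r is 0.8 to 0.5, and 20% of an effect confined to one visit.

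The power loss depends on the assumed d and r, and runs from modest to severe. The failure to test the visit-specific hypothesis depends on neither. The pilot illustration rests on ten subjects in one group and shows scale only. The plan's Aim 1 method already avoids the fault, so the two analyses are inconsistent with each other.

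**What to change.** Rewrite the Secondary Aim paragraph so that:

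- the four post-baseline visits are the responses, with the baseline value of the same indicator as a covariate (or keep baseline as a response and constrain the arms to a common baseline mean);
- visit enters as a category, with arm-by-visit terms;
- COPD severity joins the covariates, since it is a randomisation stratum;
- the tests are named: the arm contrast at week 10 for the short-term effect, and at months 3, 6 and 12 for the sustained effect, in place of the single arm p-value.

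Because this replaces one test per indicator with four, the plan should also say in advance how the later contrasts combine to support a claim of sustained effect, and how multiplicity across visits and indicators is handled.

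The cost is SAP wording, model code and that one decision. All the data are already scheduled for collection, and no extra subjects or visits are needed.
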